ALD is a thin-film deposition process for preparing high-quality oxides with atomic-layer accuracy. It offers many benefits including accurate and facile thickness control, excellent step coverage and conformality, high uniformity over a large area, low defect density, good reproducibility, and low deposition temperature. These features clearly account for the feasibility to deposit high-quality hemocompatible thin films on the whole surface of complex 3-D structures, such as the inner surface of PVC tubing in ECMO circuit, using the ALD technique.

II. Specific Aims

Surface modification of circuit material to improve the hemocompatibility

In this project, we will aim at improvement of the biocompatibility of the material used in ECMO circuit to reduce the device-induced coagulopathy. A new technique of atomic layer deposition (ALD) will be applied to coat biocompatible and hemocompatible zirconium dioxide (ZrO_2) and aluminum oxide (Al_2O_3) nanolaminate thin films on the inner (luminal) surface of ECMO circuit. The ALD technique is known to be capable of coating high-quality oxide thin films on a variety of complex surfaces. The advantages of ALD lie in its capability to produce high-quality and pinhole-free films on the surface of complicated 3-D structures with excellent uniformity and conformality as well as accurate thickness and composition control at a single atomic layer. Besides the preparation of the hemocompatible thin films on the ECMO tubing surface using ALD, surface enhanced Raman spectroscopy (SERS) is another crucial technique utilized in this subproject to optically probe the biomedical molecular characterization associated with blood coagulation and platelet activation. Moreover, the ALD technique will also be used to provide further enhancement of the functionalization, stability and reproducibility of the SERS substrates, so as to push the SERS technique into a more practical diagnostic tool in clinical monitoring. The safety and effectiveness of the newly-prepared ECMO circuit will be evaluated in the following in vitro and in vivo studies.

III. Research Design and Methods

A. Atomic Layer Deposition (ALD)

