The distinguished benefits of ALD as mentioned above can be further applied in the biomedical industry. For example, the ALD technique enables the coating of artificial implants with high-quality biocompatible thin films to minimize the impact between the implants and the biological processes inside the human body. The benefits of ALD for biocompatible coatings mainly come from the excellent conformality and uniformity together with the pinhole-free structure. Biocompatible ALD films can be used to reduce diffusion as well as improve corrosion and wear resistance. An ALD thin film only a few nanometers thick is flexible enough and thus prevent cracking, formation and spreading of detrimental

Figure 6 A batch ALD reactor with 2000 work pieces being coated simultaneously (Copyright Beneq Oy, Finland).

particles. Furthermore, ALD can be used to prepare the surface which resist bacterial growth and

accumulation of biological materials. Another advantage of ALD is that the deposition can be performed at relatively low temperatures (<150°C), thereby limiting thermal damage to the thermally fragile and temperature-sensitive substrates.

In this subproject, biocompatible and hemocompatible ZrO_2/Al_2O_3 nanolaminate thin films will be coated on the PVC tubing surface of ECMO circuit using ALD to reduce the thrombus formation. It is particularly appropriate to prepare high-quality thin films on the whole surface of complicated 3-D structures, such as the inner surface of PVC tubes, using ALD due to its high conformality. It may be noted that traditional thin-film coating techniques, including physical vapor deposition (PVD) and CVD, are unable to deposit these oxides on the inner surface of PVC tubes. The introduction of Al_2O_3 into the thin films will prevent the aging of ZrO_2 [22] and improve the adhesion to the PVC tubing surface. Other biocompatible materials, such as silicon dioxide (SiO_2), titanium dioxide (TiO_2), and titanium nitride (TiN), will be also prepared and tested to evaluate their hemocompatibility in ECMO circuit in this subproject.

C. Testing of new material

1) Physical characterization

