The thickness and dielectric constant of the ZrO_2/Al_2O_3 nanolaminate thin films will be measured using spectroscopic ellipsometry (SE). The structure of ZrO_2/Al_2O_3 nanolaminate thin films will be characterized by transmission electron microscopy (TEM), scanning electron microscopy (SEM), and X-ray photoelectron spectroscopy (XPS). Atomic force microscopy (AFM) will be used for the analysis of surface morphology and roughness.

2) Biological characterization

Basic biological evaluations following ISO 10993/EN 30993 including chemical, mechanical, thermal and aging testing of the ZrO_2/Al_2O_3 nanolaminate thin films are arranged.

3) Hemocompatibility test

Healthy non-smoking volunteers are included to donate fresh bloods via venipuncture for in vitro hemocompatibility test, while those who are pregnant, with bleeding disorders or taking anticoagulants, such as aspirin, NOAC, are excluded. A series of relevant assessments is done as the followings:

a. Serum levels of blood platelet-activating-factors

The blank PVC or PVC with T-ALD/PE-ALD Al_2O_3 films are planned to be immersed in whole blood for 1hr. The bloods are then collected and the sera were separated to determine the levels of blood platelet-activating-factors including prothrombin, sP-selectin and PAF acetylhydrolase.

b、Adhesion and morphology of blood cells

The blank PVC and Al_2O_3 -coated PVC (T-ALD and PE-ALD) samples are planned to be immersed in whole blood and incubated at 37°C for 1 hr under the static condition to check blood-surfaces adhesion. The samples are then washed gently with phosphate buffered saline (PBS), fixed with 2.5% glutaraldehyde solution for 2 hr at room temperature, and dehydrated in a gradient of ethanol/distilled water mixtures. Finally, the samples are undergone critical-point drying, and subsequently coated with gold ions and then inspected using a scanning electron microscopy.

c、Inflammatory response

After 1 hr immersion in whole blood, the inflammatory responses induced by blank PVC or surface-modified PVC samples are determined. The blood cells are collected, washed, and incubated with CD4/CD8, CD42b, CD45, or CD61/CD62P antibodies for 15 minutes on ice, and sorted using a fluorescence-activated cell sorter to evaluate the inflammatory responses.

IV. Projected Timeline

VIII. Anticipated Outcomes

A. Clinical improvement

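### The aim and the characterization concern a ZrO2/Al2O3 nanolaminate, but no blood test names it: two name only Al2O3 films and the third names no coating

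*Protocol*

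**What the plan says.** Section II (Specific Aims) sets out to "coat biocompatible and hemocompatible zirconium dioxide (ZrO_2) and aluminum oxide (Al_2O_3) nanolaminate thin films on the inner (luminal) surface of ECMO circuit", and adds: "The safety and effectiveness of the newly-prepared ECMO circuit will be evaluated in the following in vitro and in vivo studies". Section III.B repeats the choice of coating: "biocompatible and hemocompatible ZrO_2/Al_2O_3 nanolaminate thin films will be coated on the PVC tubing surface of ECMO circuit".

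The characterization follows suit. Section III.C.1 states: "The structure of ZrO_2/Al_2O_3 nanolaminate thin films will be characterized by transmission electron microscopy (TEM", followed by other methods. Section III.C.2 plans an ISO 10993 evaluation in which chemical, mechanical, "thermal and aging testing of the ZrO_2/Al_2O_3 nanolaminate thin films are arranged".

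Section III.C.3 then describes three tests on donated blood:

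- Test a (platelet-activating factors): "The blank PVC or PVC with T-ALD/PE-ALD Al_2O_3 films are planned to be immersed in whole blood for 1hr".
- Test b (adhesion and morphology): "The blank PVC and Al_2O_3 -coated PVC (T-ALD and PE-ALD) samples are planned to be immersed in whole blood".
- Test c (inflammatory response): "the inflammatory responses induced by blank PVC or surface-modified PVC samples are determined".

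Separately, Section III.B says that SiO2, TiO2 and TiN will be prepared and tested for hemocompatibility in this subproject.

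**The concern.** The film changes between characterization and blood contact, and the protocol does not say why. Al2O3 in Section III.C.3 is not described as a pilot, a surrogate or a component control; it is simply the planned test surface.

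A hemocompatibility result belongs to the surface the blood touched. If only Al2O3 films are exposed, the study has no blood data on the coating named in its aim. The physical data and the blood data would describe different films, and a statement that the nanolaminate is hemocompatible would have no direct support from these tests. Volunteers would give blood for tests whose named surfaces do not answer the stated aim.

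**Working it through.** The protocol states no figure on this point and no power calculation bears on it, so the check compares the coating named at each place.

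| Protocol section | Coating named | Nanolaminate named? |
|---|---|---|
| II, Specific Aims | ZrO2 and Al2O3 nanolaminate | yes |
| III.B, coating by ALD | ZrO2/Al2O3 nanolaminate; SiO2, TiO2 and TiN as further materials | yes |
| III.C.1, physical characterization | ZrO2/Al2O3 nanolaminate | yes |
| III.C.2, biological characterization | ZrO2/Al2O3 nanolaminate | yes |
| III.C.3.a, platelet-activating factors | Al2O3 (T-ALD, PE-ALD), against blank PVC | no |
| III.C.3.b, adhesion and morphology | Al2O3 (T-ALD, PE-ALD), against blank PVC | no |
| III.C.3.c, inflammatory response | not specified, against blank PVC | no |

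Counts:

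- Nanolaminate: named in 2 of 2 characterization sections and 0 of 3 blood tests.
- Al2O3-only film: named in 0 of 2 characterization sections and 2 of 3 blood tests.
- No coating named: 1 of 3 blood tests.
- Surfaces containing ZrO2 named anywhere in III.C.3: 0.

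Could the Al2O3 result stand in for the nanolaminate? Two things in the protocol count against it.

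1. The order of the layers is not given, so it is not stated which oxide the blood would meet.
2. The protocol's own rationale leans the other way. Section I.C.2 calls both oxides hemocompatible, but the coagulation and platelet results it reports are for ZrO2, and it is ZrO2 that it presents as a surface fit for blood contact in the tubing. Section III.B gives Al2O3 the tasks of preventing the aging of ZrO2 and improving adhesion to PVC. Tests a and b therefore name only the oxide with the supporting role.

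Could another part of the protocol fill the gap? The tests listed in III.C.2 for the nanolaminate are chemical, mechanical, thermal and aging tests; none is a blood test. Section II mentions in vivo studies, but the methods shown describe none.

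Secondary count: of the four coatings that III.B names for this subproject (nanolaminate, SiO2, TiO2, TiN), 0 of 4 are named in III.C.3.

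Size of an extended design: tests a and b each name 3 surfaces (blank PVC, T-ALD Al2O3, PE-ALD Al2O3).

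- Nanolaminate made by one ALD process: 4 surfaces, (4 − 3)/3 = 33% more.
- Nanolaminate made by both processes: 5 surfaces, (5 − 3)/3 = 67% more.

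**The case against.** The strongest reply accepts the mismatch in wording and disputes how far it reaches.

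- **Test c may cover the nanolaminate.** Its wording does not exclude it, and this stands. But test c follows directly on a and b with no new material introduced, and it measures only cell-surface markers by flow cytometry. Even on the generous reading it could not supply platelet-factor or adhesion results for the nanolaminate.
- **The evaluation may be wider than the tests shown.** Section II promises in vivo work, the list in III.C.2 is introduced as non-exhaustive, and some sections in the outline are not shown. This rightly limits the conclusion to the blood tests as written. It does not remove the contradiction, because III.C.3 reads as a continuous section and states its own test surfaces.
- **The comparison that is planned is valid.** Al2O3 against blank PVC is a sound contrast, and no donor is exposed to any coating. True: the data would be usable for Al2O3. The fault lies in what may be concluded about the coating named in the aim.
- **The other materials and the layer order are requests for detail.** This is largely fair. Section III.B does not say that SiO2, TiO2 and TiN go through these particular immersion tests. Neither item would carry the point alone.

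**Conclusion.** The concern holds. As written, blood tests a and b address Al2O3 films, test c does not identify its coating, and the hemocompatibility of the ZrO2/Al2O3 nanolaminate named in Sections II, III.B, III.C.1 and III.C.2 is not established by any of the three tests. The size is 0 of 3 blood tests naming the nanolaminate, against 2 of 2 characterization sections.

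This rests on the protocol text shown and on reading tests a and b literally. It does not depend on sample size, variance or analysis method. A statistical analysis plan could not repair it, because the choice of test surface has to be settled before the blood is exposed. It must be fixed: otherwise the aim and the named test article differ. The missing layer order and the silence of III.C.3 on SiO2, TiO2 and TiN are secondary.

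**What to change.** Reconcile the sections in one of two ways.

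1. **Test the nanolaminate.** Add the film characterized in III.C.1 and III.C.2 as a test surface in III.C.3.a, b and c, compare it with blank PVC, state its outermost layer, and name the coating in test c. The Al2O3-only films can stay as component controls. Cost: tests a and b go from 3 surfaces to 4 (33% more) or 5 (67% more). Blood per draw and assay work rise by about the same share, assuming equal blood volume per surface and one draw serving all surfaces. The protocol gives no donor number or blood volume, so the effect on donors cannot be stated.
2. **Restrict the claim to Al2O3.** If blood will meet only Al2O3 films, restate Sections II, III.B, III.C.1 and III.C.2 and all conclusions for Al2O3, characterize that film, and name it in test c. Cost: mainly wording and a change in which film is characterized, but the study may then conclude less.

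In either case, say in III.C.3 whether SiO2, TiO2 and TiN are tested in blood, or revise the sentence in III.B.

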PVC is the currently-used material in the ECMO blood tubing. Although it possesses unique physical and chemical properties, PVC was developed primarily for industrial use and later found their applications in biomedicine. Thus this synthetic material exhibits the incompatibility with blood and tissues. As in direct contact with blood, PVC is still prone to initiate the formation of clots, as the platelets and blood coagulation system are activated [16]. Besides, potential health hazards associated with the release of the plasticizer di-2(ethylhexyl)phthalate (DEHP) from the (PVC) tubing exist [17]. The lipid content of the liquid the PVC is in contact with, the temperature, and the duration of contact affects the leaching of DEHP with the greatest concern on the male reproductive system [18].

2) ZrO_2 and Al_2O_3 are well-known biocompatible and hemocompatible materials

In this subproject, ZrO_2 and Al_2O_3 are chosen as the thin-film materials deposited on the inner surface of ECMO circuit to reduce the thrombus formation because of its excellent biocompatibility. ZrO_2 and Al_2O_3 are well-known biocompatible materials which have been widely utilized in artificial implants such as ears, teeth and joints, etc. They exhibit excellent material properties for biocompatible coating including good chemical resistance and dimensional stability, high wear resistant and hardness, zero water absorption, and noncorrosivity in saline environments. Recent researches have reported that ZrO_2 can be safely used as an excellent hemocompatible material in the right ventricular assist device [19]. Results of coagulation assays and platelet aggregation tests for the ZrO_2 implants showed no device-induced hemolysis or increase in platelet activation. In addition, biological depositions or wear were not observed on the ZrO_2 surface, indicating excellent biocompatibility and hemocompatibility. These results clearly demonstrate that ZrO_2 can be used safely and effectively as a blood-contacting tubing surface in ECMO circuit to improve the blood

compatibility. However, despite the broad applications of ZrO_2 and Al_2O_3 in artificial implants, traditional thin-film coating techniques are unable to deposit these hemocompatible materials on the inner surface of the PVC tubes in ECMO circuit.

D. Atomic layer deposition (ALD)

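### Serum is named as the specimen for prothrombin and sP-selectin; followed literally, clotting in every arm can hide a coated-versus-blank difference, and item a does not fit item c

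*Protocol*

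**What the plan says.** Protocol section III.C.3 (Hemocompatibility test) describes three in vitro assays on volunteers' blood: "Healthy non-smoking volunteers are included to donate fresh bloods via venipuncture for in vitro hemocompatibility test".

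Item a is headed "Serum levels of blood platelet-activating-factors". The contact step reads: "The blank PVC or PVC with T-ALD/PE-ALD Al_2O_3 films are planned to be immersed in whole blood for 1hr". The blood is then collected and "the sera were separated to determine the levels of blood platelet-activating-factors including prothrombin, sP-selectin and PAF acetylhydrolase". Serum is thus named twice, in the heading and in the procedure.

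The section mentions anticoagulants only among the reasons for not accepting a donor: "while those who are pregnant, with bleeding disorders or taking anticoagulants, such as aspirin, NOAC, are excluded". It does not say whether the blood, once drawn, is anticoagulated, or whether activation is stopped at the end of contact.

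Item c also starts from whole blood after one hour with blank or modified PVC. There the blood cells are collected, washed, stained with antibodies (CD62P among them) and sorted by flow cytometry.

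**The concern.** The assay is meant to show whether the coating reduces activation by the surface. Section I.C.1 states the problem with the uncoated material: "PVC is still prone to initiate the formation of clots, as the platelets and blood coagulation system are activated". Preparing serum sets off the same two processes, coagulation and platelet activation, in every tube after the surface has acted.

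The coated-versus-blank comparison of prothrombin and sP-selectin may then show a smaller difference than the surfaces produced, or none. If the difference is gone from the sample, no analysis brings it back. For that reason an analysis plan written later could not repair the choice: the specimen is fixed at the bench.

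**Working it through.** The protocol states no figure to reproduce. It gives no donor number, effect size, standard deviation or assay limit for item a. The check therefore sets the texts side by side and then uses symbols to show what clotting does to a difference. That serum follows clotting, that clotting converts prothrombin and that it makes platelets release P-selectin is general laboratory knowledge, not taken from the protocol.

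**1. The two items compared**

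| | Item a | Item c |
|---|---|---|
| Starting material | whole blood, 1 h contact | whole blood, 1 h contact |
| Surfaces | blank, T-ALD, PE-ALD | blank, surface-modified |
| What is taken | serum | washed, sorted blood cells |
| State of blood required | clotted | not clotted |
| Anticoagulant stated | no | no |

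Taken literally, the two items need blood in opposite states. They agree if the blood is anticoagulated and the sera are plasma, or if the two items use separately prepared blood. The protocol states neither.

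**2. Prothrombin, if serum is really used**

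Let P_B and P_C be the amounts left at the end of contact in the blank and coated arms, and let clotting leave a fraction f.
- The serum values are f·P_B and f·P_C. Their ratio is P_C/P_B, so a constant proportional loss costs nothing on the ratio scale.
- The absolute difference is f·(P_C − P_B). It shrinks with f, which matters if assay noise does not shrink too.
- If both values fall below the assay limit, both read as the limit and the difference disappears (a floor).
- If f varies independently from tube to tube, a paired log ratio gains variance 2·Var(ln f).

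**3. sP-selectin, if serum is really used**

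Let T be the total pool, S_B and S_C the amounts released by the end of contact, and r the fraction of the remainder that clotting releases.
- The serum value is S + r·(T − S) = (1 − r)·S + r·T.
- The difference between arms is (1 − r)·(S_B − S_C): unchanged at r = 0, absent at r = 1 (a ceiling).

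**4. Direction**

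With the same f and r in all arms, neither expression changes sign. The effect is a loss of sensitivity and not a shift towards one surface.

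**5. Size**

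None of f, r, their variation or the assay limit is in the protocol. The possible loss runs from none to complete, and the document does not narrow that range.

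**The case against.** The strongest reply is that the sera are plasma, loosely named. Item c supports this, because clotted blood does not readily give a cell suspension that can be washed and sorted. The reading is plausible, but the protocol does not state it, nor does it say that items a and c share one blood preparation. A laboratory following item a as written would make serum. On the harmless reading the specimen is still misnamed, so the text needs a correction either way.

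A second reply is that plasma may be no better. An anticoagulant present during contact suppresses some of the activation that the surface would cause. If it damps the sP-selectin difference by a fraction d, with noise otherwise equal, plasma does better than serum only when d is less than r. This stands, and it is the real cost of the fix. Likewise, if the blood is not anticoagulated now, clotting during the contact hour may itself be partly the surface response. What is lost is the difference erased once every tube has clotted fully.

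A third reply is that platelet activation is still tested elsewhere, through adhesion in item b and CD62P in item c. That also stands and limits the weight of the point.

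A reader might infer that the serum step confounds the comparison or favours the coating. The documents do not support that, since the step is common to all arms. Nor do they support saying that the hemocompatibility study as a whole fails, or quoting a loss of power or a number of extra donors.

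**Conclusion.** The point holds in a limited, conditional form. Item a fixes serum as the specimen, which is a poor stated choice for prothrombin and sP-selectin and not a detail left to another document. If followed literally, it can hide a coated-versus-blank difference in those two markers, without favouring an arm. As written, it also does not fit item c unless the blood is anticoagulated or prepared separately.

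The reach is two of three soluble markers in one of three assays. PAF acetylhydrolase and the results of items b and c are not affected. The size cannot be given. The conclusion assumes that serum means what it normally means and that the clotting step is the same in all arms. If the blood is in fact anticoagulated, the fault is one of wording only. The point is worth correcting because the correction is small and a difference lost in the sample cannot be recovered.

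**What to change.** In section III.C.3, item a, replace serum and sera, for prothrombin and sP-selectin only, with wording such as: *At the end of the 1 h contact, plasma is separated from blood handled with the same anticoagulant or stop solution in all arms, and prothrombin and sP-selectin are determined in it.* Name that anticoagulant or stop solution, say whether it is present during contact or added at the end, and reconcile this with the blood used in item c. Leave PAF acetylhydrolase as written.

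Cost: a different collection tube or a stop solution, a centrifugation step, and one further aliquot per arm if PAF acetylhydrolase stays in serum. No extra volunteers are needed for the change itself. The laboratory must also choose and check the anticoagulant level, because one present during contact may damp part of the surface response equally in all arms. If the blood is already anticoagulated, only the words change.

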ECMO is well known to cause coagulopathy. High extracorporeal blood flow (BF) along with the large artificial surfaces of ECMO circuit can trigger serial cascades of inflammatory response including coagulation, complement, cytokines and eicosanoid systems with crosstalk among them [4]. The continuous activation of the contact and fibrinolytic systems as well as consumption and dilution of factors occurs within minutes of initiation of ECMO [5]. Platelets adhere to surface fibrinogen and are activated and the resultant platelet aggregation and clumping causes numbers to drop [6]. Correction by platelet transfusion produces only a temporary increase in numbers. Prolonged duration of ECMO exacerbates these

negative effects rendering the critically ill patients at more potential risks of coagulopathy, either bleeding or thrombosis.

Bleeding can rapidly become life-threatening and appears to be out of proportion to the degree of coagulopathy and patient platelet count. Cannulation (7-20%) and surgical site bleeding (6-34%) are common. Intracranial bleeding (1-11%), especially in neonates, gastrointestinal haemorrhage (1-4%), and pulmonary haemorrhage (4-8%) may also occur [7]. Concurrently, extensive thrombosis will not only interfere with the blood flow in the ECMO circuit leading to frequent tube changes, but also cause more devastating systemic complications, such as disseminated intravascular coagulopathy (DIC), cerebrovascular accident, pulmonary embolism, end organ failure, etc. Hemolysis is another well-recognized complication of ECMO with an incidence of between 5% and 8% and can reciprocally aggravate the coagulopathy [8]. The free Hb is monitored as the indicator for screening the microthrombosis in the circuit.

B. Current efforts to decrease the coagulopathy

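### Does the lack of a platelet count in the flow-cytometry assay undermine the CD62P comparison of blank and coated PVC?

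*Protocol*

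**What the plan says.** Protocol III.C.3) sets out three laboratory assays on volunteers' blood.

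- **Assay a** measures serum markers after 1 hour: "levels of blood platelet-activating-factors including prothrombin, sP-selectin and PAF acetylhydrolase".
- **Assay b** looks at adhesion by scanning electron microscopy. Blank, T-ALD and PE-ALD samples are "immersed in whole blood and incubated at 37°C for 1 hr under the static condition to check blood-surfaces adhesion".
- **Assay c** is the one in question: "After 1 hr immersion in whole blood, the inflammatory responses induced by blank PVC or surface-modified PVC samples are determined". The handling is then given in one sentence: "The blood cells are collected, washed, and incubated with CD4/CD8, CD42b, CD45, or CD61/CD62P antibodies for 15 minutes on ice", after which the cells are "sorted using a fluorescence-activated cell sorter to evaluate the inflammatory responses".

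Assay c does not say whether the cells come from the surrounding blood or off the sample. It names no cytometry measure (percent positive, intensity or count) and gives no platelet count before or after immersion.

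The Background supplies the mechanism behind the worry. Section I.A.2), on ECMO circuits in use, says: "Platelets adhere to surface fibrinogen and are activated and the resultant platelet aggregation and clumping causes numbers to drop". Section I.C.1) says of the control material that "PVC is still prone to initiate the formation of clots, as the platelets and blood coagulation system are activated".

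**The concern.** No step detaches cells from the sample, so the natural reading is that assay c examines the cells that did not stick. On the protocol's own account, platelets that meet PVC become activated, adhere and clump. The worse surface could then remove the very platelets that carry CD62P, and the remaining cells would look less activated than the blood really was. Blank PVC would be flattered and the coating's benefit understated. With heavy enough selective loss, the coating could even look worse than the control.

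A count not taken at the bench cannot be created later by an analysis plan, so this is not something to leave to a SAP. Without platelet recovery by surface, a null CD62P result would be hard to interpret.

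**Working it through.** **Inputs.** The protocol gives no activation rate, platelet loss, sample area or blood volume, so there is no figure of its own to reproduce. Every value below is an assumption chosen to show the range.

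- True activated share *a*: 30% on blank, 20% on coated (true difference 10 points).
- Share of activated platelets held on the surface *h*: 10% on coated; 30% or 50% on blank.
- Share of resting platelets held *r* = *k·h*, with *k* = 0, 0.5 or 1.

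**Formula.** Observed CD62P-positive share among the platelets left = *a*(1−*h*) / [*a*(1−*h*) + (1−*a*)(1−*r*)]. Total platelet loss = *a·h* + (1−*a*)·*r*.

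**Coated, h = 0.10**
- *k* = 0: 0.18/(0.18+0.80) = 18.4%
- *k* = 0.5: 0.18/(0.18+0.76) = 19.1%
- *k* = 1: 20.0%

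**Blank, h = 0.30**
- *k* = 0: 0.21/(0.21+0.70) = 23.1%
- *k* = 0.5: 0.21/(0.21+0.595) = 26.1%
- *k* = 1: 30.0%

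**Blank, h = 0.50**
- *k* = 0: 0.15/(0.15+0.70) = 17.6%
- *k* = 0.5: 0.15/(0.15+0.525) = 22.2%
- *k* = 1: 30.0%

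**Apparent difference, blank minus coated (true value 10 points)**

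| Activated platelets held on blank | k = 0 | k = 0.5 | k = 1 |
|---|---|---|---|
| 30% | 4.7 | 6.9 | 10.0 |
| 50% | −0.7 | 3.1 | 10.0 |

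**Where the sign reverses.** Setting the blank share equal to the coated share:
- *k* = 0: *h* = 0.475 on blank. Total loss is 0.30 × 0.475 = 14.3% on blank, against 0.20 × 0.10 = 2.0% on coated.
- *k* = 0.5: *h* = 0.618 on blank. Total loss is 0.30 × 0.618 + 0.70 × 0.309 = 40.2% on blank, against 0.20 × 0.10 + 0.80 × 0.05 = 6.0% on coated.
- *k* = 1: it never reverses.

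**The opposite case.** Let the coating hold more: 50% of activated platelets on coated, 10% on blank, *k* = 0. Blank reads 0.27/(0.27+0.70) = 27.8% and coated 0.10/(0.10+0.80) = 11.1%, a difference of 16.7 points. A second assumed pair (30% and 15% activated, true difference 15 points) with the same losses gives 27.8% and 8.1%, a difference of 19.7 points.

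**Would a count repair it?** A count gives the total loss but not how many of the lost platelets were activated. Treating all of them as activated, at *k* = 0.5 with 50% held on blank and 10% on coated, gives:
- blank: 0.15 + (0.30 × 0.50 + 0.70 × 0.25) = 47.5%
- coated: 0.18 + (0.20 × 0.10 + 0.80 × 0.05) = 24.0%

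The difference is then 23.5 points against a true 10, an error in the other direction.

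**What the bias requires.** All four of these must hold, and the protocol states none of them:
1. the cells are those left in the surrounding blood;
2. the measure is a percentage positive, or something similarly affected by selective loss;
3. activated platelets are lost faster than resting ones;
4. the loss is material on a sample of unstated size.

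**The case for a change.** The strongest case for a change is that it costs little. Stating the cell source and recording a platelet count before and after immersion needs two sentences and no extra procedure for volunteers. Assay b is microscopic inspection with no stated adherent-cell count or scored area, and assay a measures a serum marker; neither gives platelet recovery for the assay c aliquot. The ratio of platelet events (CD61 or CD42b) to CD45 events could serve as a rough check. But no such check is planned, and the stains are joined by *or*, so co-staining is not assured.

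Much of this stands. Selective loss cannot be quantified or corrected from assay c as described, and a count would help a reader interpret CD62P. What does not stand is the step from there to a fault in the plan. Differential adhesion is the premise of the concern, and assay b is there to look at it on the same kinds of surface, also after 1 hour in whole blood. The Background statement about falling platelet numbers concerns a running circuit; the only incubation condition stated for these assays is the static one in assay b. Nothing shows that loss would approach the 14.3% or 40.2% at which the sign turns in the illustration.

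**Conclusion.** No change is called for. The protocol makes no claim about platelet recovery, names no primary endpoint and ties no decision rule to CD62P. CD61/CD62P is one of several stains in one of three complementary assays. No stated rule or number is shown to give a wrong result. What is missing is bench detail (cell source, recovery, cytometry measure) that a laboratory would settle in its working procedure.

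The size of any effect is unknown. Under the assumed values a true 10-point difference appears as −0.7 to 10.0 points if blank PVC holds more activated platelets, is unchanged under equal-rate loss, and widens to 16.7 points if the coating holds far more. In the direction that the Background suggests, the bias works against the coating, so it would hide a benefit rather than create one. In the opposite direction the coated surface would carry the heavier adhesion, which assay b sets out to examine. The proposed count would reveal loss without correcting the CD62P share. A laboratory may well choose to take one, and CD62P should in any case be read alongside assays a and b.

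This conclusion rests on assay c remaining one supporting readout among three. It would need another look if CD62P alone were made the basis for claiming or rejecting an effect of the coating.
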